breach of confidentiality. Our research team is trained and experienced in the ethics of medical research and operating procedures will be enforced to insure that all subject interactions are treated confidentially and all data are protected by use of only a unique study ID number to identify the subject. Furthermore, the University of Pennsylvania has developed policies and guidelines to ensure HIPAA compliance in the collection of research data. Compliance for research data will be reviewed by the IRB as part of the human subjects approval process. The investigators will assure that the data collection instruments and consent forms are in compliance with Penn policies in this area. We are particularly sensitive to the issues of subject confidentiality with respect to HIV and depression. Consequently, we have adapted extensive procedures for our HIV and depression studies and will adapt similar procedures for the proposed study. We are committed to a system that maximally protects the confidentiality of our subjects. All subjects who consent to participation in this study receive a research identification number. Only this number, not subject name, will identify the subject in all research records. In no case will names or other personal identifiers such as social security numbers be used. The majority of data collected in this study will be entered in real time directly into the study's REDCap (Research Electronic Data Capture) database, a password-protected on-line database. Only authorized staff working on the study will have access to this database. All hard copy data will be stored separately from documents with identifying information, such as signed informed consent forms, in locked file cabinets. The security and confidentiality of the data in paper and hard copy form will be the responsibility of the P.I. Access to these locked file cabinets will be limited to the research staff under the supervision of [name] or the study coordinator.

Sensitive Research Information*

Does this research involve collection of sensitive information about the subjects that should be excluded from the electronic medical record?

No

Subject Privacy

Privacy refers to the person's desire to control access of others to themselves. Privacy concerns people, whereas confidentiality concerns data. Describe the strategies to protect privacy giving consideration to the following: The degree to which privacy can be expected in the proposed research and the safeguards that will be put into place to respect those boundaries. The methods used to identify and contact potential participants. The settings in which an individual will be interacting with an investigator. The privacy guidelines developed by relevant professions, professional associations and scholarly disciplines (e.g., psychiatry, genetic counseling, oral history, anthropology, psychology).

The research team has considerable experience relating to depressed and HIV infected subjects and understands and respects the need for patient privacy. We anticipate being able to maintain a high degree of privacy in this research project and will do everything we can to protect the privacy of individuals participating in this research. The consenting process will take place in a closed private setting or via a remote method per IRB guidance issued on 5/22/2020, such as REDCap and/or telephone or video call. All assessment visits will be kept as private as possible and generally will happen in a closed private office or via a private telephone or video call. If and when the study coordinator or study recruiter calls a subject they will only leave their name and a phone number. They will not leave anything in a message that could identify the study, or department, or status of the subject. Study procedures conducted remotely (such as informed consent, psychiatric evaluations, cognitive therapy sessions, etc.) will be conducted via either a private video or phone call. Procedures conducted through REDCap (such as informed consent or completing survey questionnaires) will be private because the study team will generate a secure survey to be sent to and completed by the participant.

Data Disclosure

Will the data be disclosed to anyone who is not listed under Personnel?

No, unless we are required by law to disclose specific data.

Data Protection*

- x **Name**
- x **Street address, city, county, precinct, zip code, and equivalent geocodes**
- x **All elements of dates (except year) for dates directly related to an individual and all ages over 89**
- x **Telephone and fax number**
- x **Electronic mail addresses**
- x **Social security numbers**
- x **Medical record numbers**
 - Health plan ID numbers**
 - Account numbers**
 - Certificate/license numbers**
 - Vehicle identifiers and serial numbers, including license plate numbers**
 - Device identifiers/serial numbers**
 - Web addresses (URLs)**
 - Internet IP addresses**
 - Biometric identifiers, incl. finger and voice prints**
 - Full face photographic images and any comparable images**
 - Any other unique identifying number, characteristic, or code**
- None**

Does your research request both a waiver of HIPAA authorization for collection of patient information and involve providing Protected Health Information ("PHI") that is classified as a "limited data set" (city/town/state/zip code, dates except year, ages less than 90 or aggregate report for over 90) to a recipient outside of the University of Pennsylvania covered entity?

No

Tissue Specimens Obtained as Part of Research*

Are Tissue Specimens being obtained for research?

Yes

Tissue Specimens - Collected during regular care*

Will tissue specimens be collected during regulator clinical care (for treatment or diagnosis)?

No

Tissue Specimens - otherwise discarded*

Would specimens otherwise be discarded?

No

Tissue Specimens - publicly available*

Will tissue specimens be publicly available?

No

Tissue Specimens - Collected as part of research protocol*

Will tissue specimens be collected as part of the research protocol?

Yes

Tissue Specimens - Banking of blood, tissue etc. for future use*

Does research involve banking of blood, tissue, etc. for future use?

Yes

Genetic testing

If genetic testing is involved, describe the nature of the tests, including if the testing is predicative or exploratory in nature. If predictive, please describe plan for disclosing results to subjects and provision

of genetic counseling. Describe how subject confidentiality will be protected Note: If no genetic testing is to be obtained, write: "Not applicable."

Not Applicable

Consent

1. Consent Process

Overview

The PI or his designee will review all study procedures and answer all questions that a potential study subject has. Only after the study has been explained thoroughly will the study staff offer the subject to sign the Informed consent. This will take place in one of the research offices used by this study on the UPENN campus (TBD), on our Mobile Clinical Trials Unit, via a private telephone or video call and/or via REDCap. The PI/ or designee will explain the study using lay language. If a subject is not capable of providing consent they will not be consented into this study. Under no circumstance will study staff try to unduely influence a subject to consent.

Children and Adolescents

Not Applicable

Adult Subjects Not Competent to Give Consent

Adult subjects not competent to give consent will not be eligible to participate in the study.

2. Waiver of Consent

Waiver or Alteration of Informed Consent*

No Waiver Requested

Minimal Risk*

Impact on Subject Rights and Welfare*

Waiver Essential to Research*

Additional Information to Subjects

Written Statement of Research*

No

If no written statement will be provided, please provide justification

The following documents are currently attached to this item:

There are no documents attached for this item.

Risk / Benefit

Potential Study Risks

All potential risks that might occur as a result of the participation in this study are detailed in the Informed Consent form and will be fully discussed with each subject by the research staff. General: It will be explained to each subject that in the event of physical injury directly resulting from the research procedures, every effort will be made to make available the facilities and professional skills of the University of Pennsylvania Health System. It will be further explained that while some risks are not predictable, every precaution consistent with the best medical practice to protect the health and safety of the subjects will be taken. We will explain to each subject that participation in the research study is completely voluntary. The subject has the right to refuse participation or withdraw at any point in the

study, without influencing any aspect of medical treatment that they may require. Medication and Placebo Use: The study clinicians will closely monitor subjects for adverse effects throughout the trial. Adverse effects can be treated by lowering the dose, or discontinuing it when necessary. Although there are no clinically proven adverse effects associated with escitalopram with regard to pregnancy, as a safety precaution we will not study pregnant women. All consenting females of childbearing potential will be tested for pregnancy prior to receiving treatment. They will be required to use an effective contraceptive method during the trial (such as a condom with spermicide or diaphragms with spermicide; oral, injectable, or implantable birth control; intrauterine devices (IUDs); surgical sterility). This will be explained in the consent form. There are no reported drug-to-drug interactions between escitalopram and antiretrovirals. However there are few clinical trials using the particular combination of agents our study participants will be on; therefore, the lack of reported interactions does not ensure that previously unknown adverse effects will not arise. Nonetheless, escitalopram is not known to have any significant effects on the cytochrome p450 isoenzyme system and no drug interaction effects are anticipated. Adverse effects will be monitored vigilantly. All serious adverse events will be fully documented and reported to the Penn IRB within 24hrs of knowledge of the event. The following safety procedures will be maintained in order to identify the presence of worsening depressive symptoms. A careful clinical psychiatric assessment, including the HAM-D scale, which is a sensitive symptom severity rating instrument, and the C-SSRS, which measures suicidal ideation, will be obtained at each assessment study "visit" whether conducted in person or remotely via private video or telephone call. In addition, study subjects will be instructed by the study clinicians about the signs and symptoms of worsening depression, and will be instructed to call the study in the event that they experience these symptoms. Information about depressive symptoms will be provided to all subjects at the beginning of the study and throughout the course of the study to enhance patient safety and study compliance. Subjects will be provided with a 24-hour emergency phone number in case of untoward events or worsening depressive symptoms. The magnitude and frequency of the clinical monitoring schedule during all aspects of the study should easily permit the study clinicians to determine the presence of symptomatic worsening. Rapid clinical intervention will be instituted in the event of significant clinical worsening. In this event, the subject will be treated as clinically warranted. Given these safeguards, we believe that the use of a placebo condition is safe when applied in accordance with the proposed treatment guidelines of our study. Risk of Computer-assisted Cognitive Behavior Therapy (CCBT): There are no known or foreseeable risks associated with receiving treatment with computer-assisted cognitive behavior therapy. Like other treatments for depression, CCBT is not effective therapy for all people and there is a chance depressive symptoms could worsen. The safeguards noted above reduce risk associated with symptomatic worsening. Risk of Phlebotomy: The potential risk of an approximately 70cc blood draw are minimal, and include the discomfort of an IV, a bruise, or rarely, an infection of the vein. To reduce these risks, blood will be collected by an experienced phlebotomist following aseptic procedures. Risk of Psychological Evaluation: Although the potential psychological risks are also minimal, participation in psychiatric interviews and psychiatric and psychological questionnaires can, for some subjects, be psychologically provocative. We will make every effort to be sensitive to the psychological response to the assessments of each individual subject. Specifically the research associates will inquire about each subjects psychological experience during each assessment. In rare instances where psychological and psychiatric evaluation evokes distressful feelings we will provide support as needed and appropriate. If a subject becomes very seriously or suicidally depressed there is a rescue procedure which involves breaking the blind on the study medication and providing or, if necessary, referring them for appropriate clinical treatment.

Potential Study Benefits

All subjects may benefit from the comprehensive medical and psychiatric diagnostic assessments in the study. Half of the depressed subject in the study will receive CCBT and antidepressant medication for their depression and will be monitored weekly (weeks 0-6) or biweekly (weeks 6-10). The other half of the depressed subjects will receive CCBT and placebo but will also be monitored weekly (weeks 0-6) or biweekly (weeks 6-10). Based on previous studies, we expect that ~ 60% of the depressed subjects receiving placebo will see an improvement in their depression. The ~40% that do not see an improvement will be referred for treatment after their participation in the study is completed. All subjects in the study will be referred for treatment of their depression and will receive follow-up to maximize treatment initiation, and or continuation. All subjects will receive free of charge medical, neurologic, immunologic and psychiatric assessments. Any subject needing immediate medical treatment, including psychiatric treatment will be referred for treatment. Being evaluated weekly/biweekly, the risks to subjects in this study are minimal and reasonable compared to the benefits gained by their participation. Subjects will also make important contributions to others via the further

development of clinical information on the best treatment approach for HIV+ subjects suffering with depression. Subjects may also contribute to a better understanding of the immune mechanisms that underlie the relationship between depression and HIV disease progression. The potential immune mechanisms by which depression may influence HIV disease progression and mortality remain to be understood. Knowledge gained from this study will advance the field of HIV care by clarifying if there exists dual benefits of pharmacotherapy for clinical depression among HIV+ patients with well-controlled viral load. This knowledge, and the good it may lead to, outweighs the minimal risks associated with this study. The study will specifically show if escitalopram given to aviremic, HIV+ depressed subjects will result in: (1) immune system homeostasis, marked by less innate immune suppression and lower levels of inflammation and immune activation; (2) if improvement in depressive symptoms are associated with improvements in innate immunity and inflammation. The proposed study is designed to determine if escitalopram will upregulate innate immunity (LUNK and intracellular gamma interferon in NK cells) and downregulate inflammation (IL-6 and CRP) in depressed, aviremic HIV+ individuals. This proposal also has the potential to produce new knowledge on the depression/ endocrine/immune mechanisms that will determine whether traditional pharmacotherapy (escitalopram), might benefit HIV+ individuals.

Alternatives to Participation (optional)

The alternative to participating in this study is not to participate.

Data and Safety Monitoring

The study will be monitored by the Principal Investigator and the Data Safety Monitoring Board (DSMB). Data and Safety Monitoring Plan In order to ensure the safety of participants and the validity and integrity of the data, we will appoint a Data and Safety Monitoring Board (DSMB) whose chief function will be to ensure safe and effective conduct of the trial. The DSMB will monitor our project and serve as a reporting body to the Penn IRB. Composition of the DSMB The DSMB will consist of 3 investigators, who are external to this study, selected from a number of scientific disciplines (including, a psychiatrist, an infectious disease practitioner, and a biostatistician) needed to interpret the data and ensure patient safety. None of the board members will be directly associated with the proposed research study. Activities of the DSMB: The primary goals of the DSMB will be: - To monitor and advise on scientific and ethical issues related to the study implementation for the protection of human subjects. - To review and approve the protocol and subsequently conduct annual reviews to determine whether patient safety has been adequately safeguarded - To review procedures and decisions regarding the adequate protection of specific patients when investigators break protocol because of adverse events or clinical deterioration. - To review progress to see that enrollment goals have been met. - To monitor and advise on ethical issues related to adverse events. - To oversee the confidentiality of data, and quality of data collection, management, and analysis - To recommend if necessary, discontinuation, modification, or termination of the study based upon emerging data (in the study and literature) and evaluation of risk/benefit ratio. - When possible, to serve as the final arbiters of whether individual patients should be removed from the protocol. The DSMB will receive quarterly reports of study progress and of any adverse effects or protocol violations. The DSMB will meet once per year, or more often as needed. In event of emergencies, the DSMB may meet via teleconference. For each annual meeting, the DSMB will first meet in an open session attended by the principal investigator and co-investigators, and the project statistician. The group will first review the research protocol and plans for data safety monitoring. The group will be used to review any problems in implementing the safety plan and for suggesting any necessary modifications to the safety plan. The DSMB will then meet in a closed session for the purpose of reviewing emerging trial data. Confidentiality will be maintained by providing data without any patient identifying information to the committee. At the conclusion of the meeting, the DSMB will make recommendations to the investigators and the IRB. The DSMB will make recommendations concerning the continuation or conclusion of the study. Data Monitored by the DSMB The DSMB will monitor both safety and outcome data as part of the yearly review. Outcome evaluations will include review of data quality and timeliness, participant recruitment, accrual and retention, and review of interim masked outcome results on primary and secondary efficacy measures. Safety evaluations will include review of adverse events and weekly symptom measures for each patient. In addition to serious adverse events, the board members will be presented with all adverse event information. The DSMB will further consider external factors such as scientific and therapeutic developments that may impact the safety or the ethics of the study. Procedures for reporting Adverse Event All serious adverse events will be reported to the members of the DSMB and the IRB within 24 hours. A report of all non-serious adverse events will be provided to the board members and the IRB yearly. NIH will be informed of all actions taken by the IRB as part of its continuing review. Oversight

of DSMB The investigators will ensure that the Data and Safety Monitoring Plan is reviewed and approved by the IRB before the initiation of the study protocol. The DSMB will then provide a report to the IRB following each yearly meeting, including recommendations concerning continuation or conclusion of the study. Data Safety Management Data will be gathered using an internet-based direct-entry data system in REDCap (Research Electronic Data Capture). REDCap is a secure web-based application designed to support data capture for research studies. REDCap provides 1) an intuitive interface for validated data entry; 2) audit trails for tracking data manipulation and export procedures; 3) automated export procedures for seamless data downloads to common statistical packages; and 4) procedures for importing data from external sources. Interview data and self-report data are entered directly onto computers and/or tablets at the research sites by research study staff and study subjects respectively. When data are entered into REDCap remotely, research study staff enter data directly into REDCap. When links to self-report surveys are sent to a participant, the participant enters their own responses and submits from their own device. While their responses cannot be accessed by another person, if someone else has access to a participants email, they may see that the person is being asked questions about depression and HIV. In cases where the participant cannot complete the surveys online, a research staff member will ask them the questions and enter their answers into REDCap. Data are transmitted over a secure web connection with authentication and data logging. Password protection allows members of the research team appropriate levels of data access.

The following documents are currently attached to this item:

There are no documents attached for this item.

Risk / Benefit Assessment

The risks of participating in this study are minimal and are outweighed by the potential benefits the study has not only to each individual subject but to society at large. Subjects in this study are depressed but not receiving treatment for their depression. Whether they receive active drug or placebo they all will participate in a cognitive behavioral therapy program for their depression. Additionally, at the conclusion of their participation each subject will be referred for appropriate treatment of their depression.

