Recruitment Procedures The enrollment of 180 depressed HIV positive, cART suppressed individuals will be accomplished through the implementation of a series of structured and well-coordinated recruitment and screening activities. These activities include: 1) the use of the Penn CFAR HIV clinical registry; 2) traditional advertising via fliers and print media; 3) networking with MH and HIV clinicians, clinic staff, case managers and patients; and 4) regular presence at clinic staff meetings to provide project visibility and feedback on project enrollment. We will post the IRB approved flyers in key locations and on the PMHARC HIV Research Bulletin Board, a web site that provides a central location for posting IRB recruitment flyers. We will begin recruitment by targeting the five adult HIV clinics that operate under the umbrella of the University of Pennsylvania Health System (UPHS). The UPHS clinics serve approximately 2,000 patients each year and are linked administratively, share a common database and electronic medical record system. We will also recruit participants from the Drexel Partnership Clinic, the Temple HIV Clinic and the Lax Clinic of Philadelphia Fight. Thus, collectively the clinics from which we will be recruiting see approximately 7,500 patients each year. Recruitment will be initiated upon notice of grant award and enrollment will begin in the fourth month of the study and continue for 53 months. **Power Analysis and Sample Size Calculation for Primary Aims** We used two-sided hypothesis tests, and assumed 10% loss to attrition over the 10 weeks. We set an overall alpha level of 5% within the innate immunity and inflammation hypotheses, so each Hypothesis is tested at $\alpha=0.025$. We used the methods of Hedeker et al. (152): assuming a within person correlation of 0.6 between visits, we have 80% power to detect a linear group by time effect (from week 0 through week 10) of Cohens $d=0.42$ or higher, and 80% power to detect a main effect (from week 2 through week 10) of $d=0.41$ or higher. **Biostatistical Consideration and Analysis Plan for Primary Aims** For Primary Aims 1A and 1B, participants will provide measures of innate immunity and inflammation at baseline, and at weeks 2, 4, and 10. The measures will be continuously distributed, and we will use linear mixed effects models, probably after log transformation of a response, to estimate the effects of medication group and time on the distribution of the responses across the 10 week period. The explanatory variables in these models will be a binary indicator of medication group, variables representing time effects, together with possible group by time interaction terms. Time will be modeled as a discrete factor. For the covariance structure, we expect that a random intercept model will provide a good fit to the data, and will also compare other possible specifications using BIC comparisons. **Biostatistical Consideration and Analysis Plan for Secondary Aim First**, we will examine whether participants showing improvement in depression measures are also those showing improvement in primary biological measures. Here, we will calculate change from baseline scores for the HAM-D and for the four immunity measures. For each immunity measure and HAM-D, we will use bivariate mixed

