BDI II for subjective ratings of depressive symptoms; 5) C-SSRS to assess suicidal ideation; 6) Medical history and vital signs; 7) Neuropsychological assessment to exclude HAD; 8) HIV plasma RNA viral load test; 9) Biological assessment: comprehensive immune, virologic and neuroendocrine measures, a complete blood count (CBC), and a comprehensive metabolic panel (CMP); and 10) Pregnancy test. These procedures may happen at our research offices, remotely via private video or telephone call, or on our Mobile Clinical Trials Unit (MCTU). The SCID-RV, HAM-D, and C-SSRS will be audio recorded for training purposes on a digital audio recorder or on Bluejeans. Subjects will also sign a release of information to allow us to communicate with their HIV primary care provider. The baseline assessment may be completed in one longer visit (8-10 hours) or two shorter visits (each 4-5 hours).

Randomization The 180 HIV-seropositive eligible and consenting depressed subjects will be randomized to 10 weeks of double blind therapy with either escitalopram or placebo. Study medication may be sent to participants via mail. All participants will concurrently begin CCBT. Stratification based on race, sex, and baseline depression symptom severity, will be incorporated to ensure an even distribution of more severely depressed subjects (i.e., those with HAM-D scores greater than or equal to 20) in each treatment condition. Neither the research nurse nor the study clinicians will be aware of the assigned treatment condition for each subject nor will any research staff having any clinical contact with the study participants be aware of the treatment assignment during each subjects participation in the study. Only the research pharmacist will be unblinded to the treatment condition during each subjects participation.

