Second, we will test whether Escitalopram has direct and indirect effects on the immune responses. The primary analyses (for Aims 1A and 1B) have addressed the total effect of Escitalopram on the four immunity measures. One set of analyses will use the confidence limit approach of MacKinnon et al (135, 136), to test whether changes in Hamilton score at week 2 (and, separately, at week 4) mediate the change in immunity measures at week 10. To obtain a complete picture of the possible mediation effects of depression, we will also perform these analyses using 50% reduction in HAM-D, and HAM-D ≤ 7 , as the measures of the direct effect of Escitalopram on depression. We will perform these analyses on the four innate immunity and inflammation responses separately. These mediation analyses focus on the end of treatment time point. To obtain information on longitudinal mediation across the full period, we will use latent growth curve mediation models (MacKinnon, 2008, 8.10-8.14). These models are similar to the bivariate mixed effects models described above, but here we include additional regression terms to isolate effects of depression on immunity across time, and random intercepts and slopes for the repeated depression scores and the repeated immunity scores, with the intercept and slope of the immunity response regressed on the intercept and slope of the depression response. MacKinnon (2008) describes how the estimated coefficients of these models can be used to provide estimates and confidence intervals for the indirect and direct effects of Escitalopram on immunity.

C.3.2.b Power Analysis and Sample Size Calculation for Primary Aims

We use two-sided hypothesis tests, and assume 10% loss to attrition over the 10 weeks. We set an overall alpha level of 5% within the innate immunity and inflammation hypotheses, so each Hypothesis is tested at alpha=0.025. We use the methods of Hedeker et al (122): assuming a within person correlation of 0.6 between visits, we have 80% power to detect a linear group by time effect (from week 0 through week 10) of Cohen's $d=0.40$ or higher, and 80% power to detect a main effect (from week 2 through week 10) of $d=0.4$ or higher.

C.3.3 Expected Outcomes, Potential Problems and Alternative Approaches

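### The fixed 0.025/0.025 split is valid, but Holm's step-down would recover power within the same 5% bound once the two tests sharing it are named

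*Protocol*

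**What the plan says.** The rule stands in the protocol under Accrual, in the paragraph on power and sample size for the primary aims: "We set an overall alpha level of 5% within the innate immunity and inflammation hypotheses, so each Hypothesis is tested at" 0.025. SAP section C.3.2.b has the same rule: "so each Hypothesis is tested at alpha=0.025". The tests are two-sided.

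Neither document mentions a step-down procedure or any reuse of alpha. The analysis paragraphs for the primary aims (protocol, Accrual; SAP C.3.2.a) contain no multiplicity rule, so the sentence in the power section is all there is.

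SAP section C.3.1 gives Aim 1A two markers (LUNK and intracellular IFN-γ) and Aim 1B two markers (IL-6 and CRP). The power sections quote two contrasts, a linear group-by-time effect and a main effect over weeks 2 to 10, and do not say which is primary.

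**The concern.** Under the fixed split each hypothesis is held to 0.025 whatever the other shows. After one rejection only one null hypothesis remains, and a test of it at 0.05 keeps familywise error at 5%. The plan never uses that alpha.

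Take invented p-values of 0.020 for IL-6 and 0.040 for CRP, and suppose these two markers are the pair that shares 5%. The plan would report one positive marker; Holm would report two, under the same 5% bound.

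This matters most when both effects are real. SAP section C.3.3 expects NK function to recover and inflammatory markers to fall, so the chance of confirming both is of direct interest to this trial.

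**Working it through.** **Inputs from the documents.** Overall alpha 5%, 0.025 per hypothesis. Two-sided tests and 10% attrition ("We used two-sided hypothesis tests, and assumed 10% loss to attrition over the 10 weeks"). 180 randomized (protocol, Randomization), half to each arm (Potential Study Benefits): 180 × 0.9 = 162, or 81 per arm. Correlation between visits 0.6, taken as equal for all pairs, which matches the expected random intercept model. Measures at baseline and weeks 2, 4 and 10.

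**Input not in the documents.** The correlation r between the two test statistics, taken as 0 to 0.7.

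**The plan's own figures.**
- Alpha: 0.025 + 0.025 = 0.05.
- Main effect, d = 0.41: the SD of the mean of three visits is √((1 + 2 × 0.6)/3) = 0.856; the standard error is 0.856 × √(2/81) = 0.1346; 0.41/0.1346 − 2.241 = 0.806, which is power of 79.0%.
- Linear effect, d = 0.42, with residual variance 1 − 0.6 = 0.4: power 81.8% with equally spaced visits and 82.2% with weeks 0, 2, 4 and 10.

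Both agree closely with the stated 80%. The SAP quotes d = 0.40 for both effects. At 81 per arm that gives 76.8% (main) and 77.6–78.0% (linear). The two documents should be reconciled on this, but the comparison below starts from 80% whichever d is meant.

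**Holm against the fixed split, both effects at 80%.** The noncentrality is 2.2414 + 0.8416 = 3.083, so power at two-sided 0.05 is 86.9%, which is 6.9 points more. For independent tests:
- per test: 0.80 + 0.069 × 0.80 = 0.855, against 0.80;
- both: 0.869² − 0.069² = 0.751, against 0.80² = 0.64;
- at least one: 1 − 0.20² = 0.96 under either rule.

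Bivariate normal probabilities for correlated tests (%, fixed split → Holm):

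| r | Per test | Both | At least one (either rule) | Familywise error, both nulls true (either rule) | Error on one true null, other effect real |
|---|---|---|---|---|---|
| 0 | 80.0 → 85.5 | 64.0 → 75.1 | 96.0 | 4.9 | 2.5 → 4.5 |
| 0.3 | 80.0 → 85.0 | 66.6 → 76.6 | 93.4 | 4.8 | 2.5 → 4.4 |
| 0.5 | 80.0 → 84.6 | 68.7 → 77.8 | 91.3 | 4.7 | 2.5 → 4.2 |
| 0.7 | 80.0 → 84.1 | 71.3 → 79.4 | 88.7 | 4.3 | 2.5 → 4.0 |

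**Less favourable cases, r = 0.**
- Other hypothesis null: 0.80 + 0.069 × 0.025 = 0.802, a gain of about 0.2 point.
- Other hypothesis at 50% power: the first test goes from 80% to 83.5%, the second from 50% to 58.9%, and both from 40.0% to 52.4%.

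**Why the pair must be named.** Suppose Aims 1A and 1B share the 5% and either marker can carry its aim. Let 1A be real with 80% power per marker, let 1B be null, and let the markers be independent.
- Fixed split, error on 1B: 1 − 0.975² = 4.9%.
- Step-down: 1A is rejected with probability 0.96, after which 1B is tested at 0.05 per marker with error 1 − 0.95² = 9.75%. In total, 0.96 × 9.75% + 0.04 × 4.9% = 9.6%.

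On that reading, adding Holm without first fixing one p-value per aim nearly doubles the error on 1B.

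**The case against.** The strongest reply is that nothing is broken. An equal Bonferroni split of two tests controls error at 5%, and the sample size was planned at 0.025. That stands. A reader might infer from this point that the split is a mistake or that the 80% power is wrong; the documents support neither.

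The size of the gain is also open to challenge, and that stands in part. The headline figures assume both effects are real at full planned size. SAP section C.3.3 itself provides for finding no change in IFN-γ, in which case Holm adds almost nothing within the innate immunity pair.

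A reader might further infer that two tests share the 5% however the sentence is read. The documents do not support that. Each aim names two markers, no rule combines them, and no single contrast is primary. The IL-6 and CRP example works only if the 5% is shared within each domain. If it is shared between the aims, there is not yet one p-value per aim to order.

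Nor is Holm free in every sense. The 5% bound is unchanged, but the actual error on a single true null rises. Finally, the protocol is dated February 2021, the planned start was December 2015 with a five-year duration, and participants learn their assignment at the week 10 visit. A change that makes rejection easier this late needs a documented justification.

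**Conclusion.** The point holds as a missed efficiency. Holm rejects everything the fixed split rejects and sometimes more, and it keeps familywise error at or below 5% under any dependence. The gain is about 4 to 6 points per test and about 8 to 11 points for confirming both. That rests on two assumptions: both effects real at the planned 80%, and r between 0 and 0.7. For scale, with independent tests the fixed split would need about 18% more participants (roughly 213 instead of 180) to reach 75% for both.

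The conclusion depends on two well-defined tests sharing the 5%. The present wording does not supply them, and until it does the step-down should not be added.

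**What to change.** Make the change in the protocol's power section and SAP C.3.2.b, carry it into the analysis sections, and document it before any unblinded analysis.

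1. Name the two tests that share the 5%, with one prespecified contrast and one p-value per test. Either use the two markers within each domain, or define one p-value for each of Aims 1A and 1B. The first option holds 5% per domain, so the bound over all four markers is 5% + 5% = 10%, and the text should say so.
2. Then add: *The smaller p-value is compared with 0.025 and, if significant, the larger with 0.05.*
3. Keep the 80% figures based on 0.025 and describe them as the minimum, first-step power.

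The cost is a few sentences and a dated justification, with no extra participants or samples. Two downsides should be stated. Error on a single true null rises from 2.5% to about 4–4.5%, still within 5%. Any 97.5% interval that is reported may include zero for a second-step rejection. Neither document now specifies intervals for the primary aims, so no existing commitment is affected.
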